9.1.4. Informed Consent

The investigator is responsible for obtaining written informed consent from each individual participating in this study after adequate explanation of the aims, methods, objectives, and potential hazards of the study and before undertaking any study-related procedures. The investigator must use the most current IRB- or IEC- approved consent form for documenting written informed consent. Each informed consent (or assent as applicable) will be appropriately signed and dated by the subject or the subject's legally authorized representative and the person conducting the consent discussion, and also by an impartial witness if required by IRB/IEC or local requirements.

9.1.5. Confidentiality

The investigator must assure that subjects' anonymity will be strictly maintained and that their identities are protected from unauthorized parties. Only an identification code and any other unique identifier(s) as allowed by local law (such as year of birth) will be recorded on any form or biological sample submitted to the Sponsor, IRB or IEC, or laboratory. Laboratory specimens must be labeled in such a way as to protect subject identity while allowing the results to be recorded to the proper subject. Refer to specific laboratory instructions. NOTE: The investigator must keep a screening log showing codes, names, and addresses for all subjects screened and for all subjects enrolled in the trial. Subject data will be processed in accordance with all applicable regulations.

The investigator agrees that all information received from Gilead, including but not limited to the investigator brochure, this protocol, CRF/eCRF, the IMP, and any other study information, remain the sole and exclusive property of Gilead during the conduct of the study and thereafter. This information is not to be disclosed to any third party (except employees or agents directly involved in the conduct of the study or as required by law) without prior written consent from Gilead. The investigator further agrees to take all reasonable precautions to prevent the disclosure by any employee or agent of the study site to any third party or otherwise into the public domain.

9.1.6. Study Files and Retention of Records

The investigator must maintain adequate and accurate records to enable the conduct of the study to be fully documented and the study data to be subsequently verified. These documents should be classified into at least the following two categories: (1) investigator's study file, and (2) subject clinical source documents.

The investigator's study file will contain the protocol/amendments; CRF and query forms, as applicable; IRB or IEC and governmental approval with correspondence; informed consent; drug records; staff curriculum vitae and authorization forms; and other appropriate documents and correspondence.

The required source data should include sequential notes containing at least the following information for each subject:

- Subject identification (name, date of birth, gender);
- Documentation that subject meets eligibility criteria, i.e., history, physical examination, and confirmation of diagnosis (to support inclusion and exclusion criteria);
- Documentation of the reason(s) a consented subject is not enrolled;
- Participation in study (including study number);
- Study discussed and date of informed consent;

- Dates of all visits;
- Documentation that protocol specific procedures were performed;
- Results of efficacy parameters, as required by the protocol;
- Start and end date (including dose regimen) of IMP, including dates of dispensing and return;
- Record of all adverse events and other safety parameters (start and end date, and including causality and severity);
- Concomitant medication (including start and end date, dose if relevant; dose changes);
- Date of study completion and reason for early discontinuation, if it occurs.

All clinical study documents must be retained by the investigator until at least 2 years or according to local laws, whichever is longer, after the last approval of a marketing application in an ICH region (i.e., United States, Europe, or Japan) and until there are no pending or planned marketing applications in an ICH region; or, if no application is filed or if the application is not approved for such indication, until 2 years after the investigation is discontinued and regulatory authorities have been notified. Investigators may be required to retain documents longer if specified by regulatory requirements, by local regulations, or by an agreement with Gilead. The investigator must notify Gilead before destroying any clinical study records.

Should the investigator wish to assign the study records to another party or move them to another location, Gilead must be notified in advance.

If the investigator cannot provide for this archiving requirement at the study site for any or all of the documents, special arrangements must be made between the investigator and Gilead to store these records securely away from the site so that they can be returned sealed to the investigator in case of an inspection. When source documents are required for the continued care of the subject, appropriate copies should be made for storage away from the site.

9.1.7. Case Report Forms

For each subject consented, an eCRF will be completed by an authorized study staff member whose training for this function is documented according to study procedures. eCRF should be completed on the day of the subject visit to enable the sponsor to perform central monitoring of safety data. The Eligibility Criteria eCRF should be completed only after all data related to eligibility have been received. Subsequent to data entry, a study monitor will perform source data verification within the EDC system. Original entries as well as any changes to data fields will be stored in the audit trail of the system. Prior to database lock (or any interim time points as described in the clinical data management plan), the investigator will use his/her log in credentials to confirm that the forms have been reviewed, and that the entries accurately reflect the information in the source documents. The eCRF captures the data required per the protocol schedule of events and procedures. System-generated or manual queries will be issued to the

investigative site staff as data discrepancies are identified by the monitor or internal Gilead staff, who routinely review the data for completeness, correctness, and consistency. The site coordinator is responsible for responding to the queries in a timely manner, within the system, either by confirming the data as correct or updating the original entry, and providing the reason for the update (e.g., data entry error). At the conclusion of the trial, Gilead will provide the site with a read-only archive copy of the data entered by that site. This archive must be stored in accordance with the records retention requirements outlined in Section 9.1.6.

9.1.8. Investigational Medicinal Product Accountability and Return

Gilead recommends that used and unused IMP supplies be returned to the shipping facility from which it came for eventual destruction. The study monitor will provide instructions for return. If return is not possible, the study monitor will evaluate each study center's IMP disposal procedures and provide appropriate instruction for destruction of unused IMP supplies. If the site has an appropriate standard operating procedure (SOP) for drug destruction as determined by Gilead QA, the site may destroy used (empty or partially empty) and unused IMP supplies in accordance with that site's approved SOP. A copy of the site's approved SOP will be obtained for central files.

If IMP is destroyed on site, the investigator must maintain accurate records for all IMP destroyed. Records must show the identification and quantity of each unit destroyed, the method of destruction, and the person who disposed of the IMP. Upon study completion, copies of the IMP accountability records must be filed at the site. Another copy will be returned to Gilead.

The study monitor will review IMP supplies and associated records at periodic intervals.

9.1.9. Inspections

The investigator will make available all source documents and other records for this trial to Gilead's appointed study monitors, to IRBs or IECs, or to regulatory authority or health authority inspectors.

9.1.10. Protocol Compliance

The investigator is responsible for ensuring the study is conducted in accordance with the procedures and evaluations described in this protocol.

9.2. Sponsor Responsibilities

9.2.1. Protocol Modifications

Protocol modifications, except those intended to reduce immediate risk to study subjects, may be made only by Gilead. The investigator must submit all protocol modifications to the IRB or IEC in accordance with local requirements and receive documented approval before modifications can be implemented.

9.2.2. Study Report and Publications

A clinical study report (CSR) will be prepared and provided to the regulatory agency. Gilead will ensure that the report meets the standards set out in the ICH Guideline for Structure and Content of Clinical Study Reports (ICH E3). Note that an abbreviated report may be prepared in certain cases.

Investigators in this study may communicate, orally present, or publish in scientific journals or other scholarly media only after the following conditions have been met:

- The results of the study in their entirety have been publicly disclosed by or with the consent of Gilead in an abstract, manuscript, or presentation form or the study has been completed at all study sites for at least 2 years.
- The investigator will submit to Gilead any proposed publication or presentation along with the respective scientific journal or presentation forum at least 30 days before submission of the publication or presentation.
- No such communication, presentation, or publication will include Gilead's confidential information (see Section 9.1.5).

The investigator will comply with Gilead's request to delete references to its confidential information (other than the study results) in any paper or presentation and agrees to withhold publication or presentation for an additional 60 days in order to obtain patent protection if deemed necessary.

9.3. Joint Investigator/Sponsor Responsibilities

9.3.1. Payment Reporting

Investigators and their study staff may be asked to provide services performed under this protocol, e.g., attendance at Investigator's Meetings. If required under the applicable statutory and regulatory requirements, Gilead will capture and disclose to Federal and State agencies any expenses paid or reimbursed for such services, including any clinical trial payments, meal, travel expenses or reimbursements, consulting fees, and any other transfer of value.

9.3.2. Access to Information for Monitoring

In accordance with regulations and guidelines, the study monitor must have direct access to the investigator's source documentation in order to verify the accuracy of the data recorded in the CRF/eCRF.

The monitor is responsible for routine review of the CRF/eCRF at regular intervals throughout the study to verify adherence to the protocol and the completeness, consistency, and accuracy of the data being entered on them. The monitor should have access to any subject records needed to

verify the entries on the CRF/eCRF. The investigator agrees to cooperate with the monitor to ensure that any problems detected through any type of monitoring (central, on site) are resolved.

9.3.3. Access to Information for Auditing or Inspections

Representatives of regulatory authorities or of Gilead may conduct inspections or audits of the clinical study. If the investigator is notified of an inspection by a regulatory authority the investigator agrees to notify the Gilead medical monitor immediately. The investigator agrees to provide to representatives of a regulatory agency or Gilead access to records, facilities, and personnel for the effective conduct of any inspection or audit.

9.3.4. Study Discontinuation

Both the sponsor and the investigator reserve the right to terminate the study at any time. Should this be necessary, both parties will arrange discontinuation procedures and notify the appropriate regulatory authority(ies), IRBs, and IECs. In terminating the study, Gilead and the investigator will assure that adequate consideration is given to the protection of the subjects' interests.

11. APPENDICES

- Appendix 1. Investigator Signature Page
- Appendix 2. Study Procedures Table
- Appendix 3. GSI Grading Scale for Severity of Adverse Events and Laboratory Abnormalities
- Appendix 4. Pregnancy Precautions, Definition for Female of Childbearing Potential, and Contraceptive Requirements

Appendix 2. Study Procedures Table

	Screening	Day 1 ^a	Treatment Week (±3 days)					Posttreatment Week (±5 days)	
			1	2	4	8	12/ET ^b	4	12
Clinical Assessments									
Informed Consent	X								
Determine Eligibility	X	X							
Medical History	X								
Physical Examination	X	X					X		
Height	X								
Weight	X	X					X		X
Vital Signs ^c	X	X	X	X	X	X	X	X	X
12 Lead ECG ^d	X	X	X				X		
Adverse Events and Concomitant Medications ^e	X	X	X	X	X	X	X	X	
Pregnancy Prevention Counseling		X					X	X	
Imaging for HCC ^f	X								
Review of Study Drug Adherence and Drug Accountability ^g			X	X	X	X	X		
Study Drug Dispensing ^h		X			X				
Laboratory Assessments									
Hematology	X	X		X	X	X	X	X	
Chemistry	X	X		X	X	X	X	X	X
Coagulation (PT, aPTT and INR)	X	X		X	X	X	X		
Urinalysis, Urine drug screen	X								
HCV RNA	X	X		X	X	X	X	X	X

	Screening	Day 1 ^a	Treatment Week (±3 days)					Posttreatment Week (±5 days)	
			1	2	4	8	12/ET ^b	4	12
HCV resistance samples		X		X	X	X	X	X	X
HBV DNA Sample ⁱ				X	X	X	X	X	X
Single PK				X	X	X	X		
Serum or Urine Pregnancy Test ^j	X	X			X	X	X	X	
Serum FSH ^k	X								
HCV Genotyping	X								
IL28B Genotype		X							
HCV Ab, HIV Ab, HBsAg, HBsAb, HBcAb	X								
HbA1c	X								
FibroTest [®]	X								

CCI

- a Day 1 assessments must be performed prior to dosing.
- b ET early termination.
- c Vital signs include resting blood pressure, pulse, respiratory rate and temperature.
- d Subjects will be required to rest in a supine position for ≥ 5 minutes prior to making a recording. The investigator (or qualified designee) should review the ECG traces recorded in real time for clinically significant abnormalities.
- e Adverse events and Concomitant Medications will be collected up to 30 days after the last dose of all study drugs.
- f Liver imaging (eg, ultrasound or CT scan, at the discretion of the investigator) should be performed to exclude the presence of hepatocellular carcinoma (HCC) within 4 months of Day 1 for subjects with cirrhosis, and within 6 months of Day 1 for subjects without cirrhosis.
- g Study drugs will be reconciled at every post Day 1 visit by the investigator in order to monitor the subject's adherence with the study drugs. Subjects must be instructed to bring back all bottles of study drugs in the original container at every post Day 1 visit through the end of treatment.
- h The IWRS will provide direction on the specifics of each subject's study drug dispensing.
- i Sample only to be collected for HBcAb positive subjects at Screening. Reflex testing done only when ALT > ULN or > Day 1 value in these subjects.
- j All females of childbearing potential will have a serum pregnancy test at Screening. Urine pregnancy testing will occur at Day 1 and every 4 weeks through posttreatment Week 4 and at ET if applicable. In the event of a positive urine pregnancy result, subjects will be instructed to return to the clinic as soon as possible for a serum pregnancy test.
- k Women of any age with amenorrhea of ≥ 12 months (see Appendix 4).

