Reference Therapy, Dose, and Mode of Administration:	None
Criteria for Evaluation:	
Safety:	AEs and safety laboratory tests will be collected throughout the study.
Efficacy:	Efficacy will be evaluated using scheduled assessments of HCV RNA performed using COBAS [®] Ampliprep/ COBAS [®] TaqMan [®] HCV Quantitative Test, version 2.0.
Pharmacokinetics:	A single PK blood sample will be collected at Weeks 2, 4, 8, 12, and Early Termination (if applicable) for all subjects.
	CCI [REDACTED]

CCI

Statistical Methods:

The primary efficacy endpoint for the study is SVR12 in all enrolled and treated subjects. No hypothesis testing will be performed.

Secondary efficacy endpoints include SVR4.

Continuous endpoints (except for safety endpoints) will be summarized using an 8-number summary (n, mean, standard deviation [SD], median, Q1, Q3, minimum, and maximum) by cohort. Categorical endpoints will be summarized by number and percentage of subjects who meet the endpoint definition by cohort.

Safety endpoints will be analyzed by the number and percent of subjects with events or abnormalities for categorical values or 8-number summary (n, mean, standard deviation, median, Q1, Q3, minimum, and maximum) for continuous data by cohort.

For Cohort 1, with approximately 50 subjects enrolled into the study, the 2-sided 95% exact confidence interval (CI) using the binomial distribution (Clopper-Pearson method) of the SVR12 rate will be from 86.3% to 99.5%, assuming the expected SVR12 rate is 95%.

For Cohort 2, with approximately 30 subjects enrolled into the study, the 2-sided 95% exact CI using the binomial distribution (Clopper-Pearson method) of the SVR12 rate will be from 82.8% to 99.9%, assuming the expected SVR12 rate is 95%.

This study will be conducted in accordance with the guidelines of Good Clinical Practice (GCP) including archiving of essential documents.

GLOSSARY OF ABBREVIATIONS AND DEFINITION OF TERMS

°C	degrees Celsius
°F	degrees Fahrenheit
Ab	antibody
ABW	actual body weight
AE(s)	adverse event(s)
ALT	alanine aminotransferase (also SGPT)
aPTT	activated partial thromboplastin time
AST	aspartate aminotransferase (also SGOT)
ASV	asunaprevir
BMI	body mass index
CCDS	Company Core Data Sheet
CFR	Code of Federal Regulations
CI	confidence interval
ClCr	creatinine clearance
CRO	contract research organization
CSR	clinical study report
DAA	direct-acting antiviral
DCV	daclatasvir
dl	Deciliter
DSV	dasabuvir
EBR	elbasvir
ECG	electrocardiogram

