6.3.1. Posttreatment Week 4 (\pm 5 Days)

The following procedures/assessments are to be completed for all subjects, 4 weeks after taking the last dose of study drug:

- Obtain vital signs (refer to Section [6.7.5](#))
- Assessment of AEs and concomitant medications
- Conduct pregnancy prevention counseling
- Obtain blood samples for tests:
 - Hematology
 - Chemistry
 - HCV RNA
 - HCV resistance samples
 - HBV DNA Sample (only for HBcAb positive subjects at Screening)
- Obtain urine sample for:
 - Pregnancy test for females of childbearing potential only (refer to Section [6.7.10](#))

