6.3.2. Posttreatment Week 12 (\pm 5 Days)

The following procedures/assessments are to be completed for all subjects, 12 weeks after taking the last dose of study drug:

- Obtain weight
- Obtain vital signs (refer to Section [6.7.5](#))
- Obtain blood samples for tests:
 - Chemistry
 - HCV RNA

HCV resistance samples

HBV DNA Sample (only for HBcAb positive subjects at Screening)

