6.6. Unscheduled Visit

A subject should attend an unscheduled visit if requested by the sponsor or the investigator. The assessments are at the investigator's discretion as clinically indicated, but the investigator should, at a minimum, collect AE and concomitant medication information. At all unscheduled visits initiated for the purpose of confirming virologic failure, a HCV resistance sample must be collected.

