6.8. End of Study

Subjects are considered to have completed the study after the posttreatment Week 12 visit, regardless of treatment duration or early termination of study drug.

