7.2.2. Assessment of Severity

The severity grading of AEs will be assessed as Grade 1, 2, 3, or 4 using the GSI Grading Scale for Severity of Adverse Events and Laboratory Abnormalities ([Appendix 3](#)). For AEs associated with laboratory abnormalities, the event should be graded on the basis of the clinical severity in the context of the underlying conditions; this may or may not be in agreement with the grading of the laboratory abnormality.

7.3. Investigator Requirements and Instructions for Reporting Adverse Events and Serious Adverse Events to Gilead or CRO:

Requirements for collection prior to study drug initiation: After informed consent, but prior to initiation of study medication, the following types of events should be reported on the case report form (eCRF): All SAEs, and adverse events related to protocol-mandated procedures.

Adverse Events

Following initiation of study medication, collect all AEs, regardless of cause or relationship, until 30-days after last administration of study IMP, and they must be reported to the eCRF database as instructed.

All AEs should be followed up until resolution or until the adverse event is stable, if possible. Gilead Sciences may request that certain AEs be followed beyond the protocol defined follow up period.

Serious Adverse Events

All SAEs, regardless of cause or relationship, that occurs after the subject first consents to participate in the study (i.e., signing the informed consent) and throughout the duration of the study, including the protocol-required post treatment follow-up period, must be reported to the eCRF database and Gilead Pharmacovigilance & Epidemiology (PVE) as instructed. This also includes any SAEs resulting from protocol-associated procedures performed after informed consent is signed.

Investigators are not obligated to actively seek SAEs after the protocol defined follow up period; however, if the investigator learns of any SAEs that occur after study participation has concluded and the event is deemed relevant to the use of IMP, he/she should promptly document and report the event to Gilead PVE.

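### SAEs must be reported through posttreatment Week 12, but the schedule's only stated limit for adverse events is 30 days and no AE or SAE enquiry is planned at the Week 12 visit

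*Protocol*

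**What the plan says.** Protocol Section 7.3 sets two collection periods. For adverse events, sites are to "collect all AEs, regardless of cause or relationship, until 30-days after last administration of study IMP". For SAEs, reporting starts at consent and runs "throughout the duration of the study, including the protocol-required post treatment follow-up period, must be reported to the eCRF database". The same section releases investigators from actively seeking SAEs only once the protocol-defined follow-up is over. Section 3.2 gives a 12-week posttreatment period, and Section 6.8 fixes its end: "Subjects are considered to have completed the study after the posttreatment Week 12 visit".

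The schedule gives one period only. Footnote e to the adverse-event row in Protocol Appendix 2 reads "Adverse events and Concomitant Medications will be collected up to 30 days after the last dose of all study drugs", and SAP Appendix 1 repeats it. In both grids that row is marked at posttreatment Week 4 and blank at posttreatment Week 12.

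The visit lists agree with the grids. Section 6.3.1 (Week 4) includes "Assessment of AEs and concomitant medications". Section 6.3.2 (Week 12) opens with "The following procedures/assessments are to be completed for all subjects, 12 weeks after taking the last dose of study drug" and then lists weight, vital signs, chemistry, HCV RNA, a resistance sample and, for HBcAb-positive subjects, an HBV DNA sample. It has no AE or SAE item.

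Elsewhere, the synopsis says "AEs and safety laboratory tests will be collected throughout the study", and Section 6.6 says that at an unscheduled visit "the investigator should, at a minimum, collect AE and concomitant medication information".

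**The concern.** Section 6 sends sites to Appendix 2 and the visit lists for what to do at each visit. A site working from them is told that adverse-event collection stops at 30 days and is not asked about SAEs at the final visit. Section 7.3 says SAE reporting continues to that visit. The schedule therefore neither states nor prompts a duty that the reporting section imposes.

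The risk is under-ascertainment of SAEs and deaths with onset after the Week 4 visit, plus a few ordinary AEs in the last days of the 30-day period. Events that are reported are not lost: SAP Section 7.1.6 lists all SAEs and deaths with a treatment-emergence flag and summarizes all deaths, whether or not treatment emergent. Those outputs can only be as complete as the ascertainment behind them. Safety is a primary objective (Protocol Section 2), and there is no data monitoring committee (Section 8.8).

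**Working it through.** The plan states no figure of its own to reproduce here. The check is a comparison of passages, followed by day counts.

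**Does the adverse-event row cover SAEs?** One could read the row and footnote e as referring to ordinary AEs only, with SAEs handled separately under Section 7.3. The Screening column rules this out. Before first dose, only SAEs and procedure-related AEs are collected (Sections 6.1.1 and 7.3), yet the row is marked at Screening. The schedule thus uses this row when ordinary AEs are out of scope, so the Week 12 blank means that no SAE enquiry is scheduled.

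**Visit windows** (nominal days 28 and 84 after last dose, ±5 days, Appendix 2):
- Week 4: 28 ± 5 = Days 23 to 33
- Week 12: 84 ± 5 = Days 79 to 89

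**Time from the last scheduled enquiry to study end:**
- nominal: 84 − 28 = 56 days
- shortest: 79 − 33 = 46 days
- longest: 89 − 23 = 66 days

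**Part of the SAE period beyond footnote e's limit:** 84 − 30 = 54 days (79 − 30 = 49 to 89 − 30 = 59). Nominally this is 54/84 = 64% of follow-up.

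**Part of the 30-day AE period after the Week 4 visit**, max(0, 30 − visit day):
- Day 23: 7 days
- Day 28: 2 days
- Day 29: 1 day
- Days 30 to 33: 0 days

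**Subject-time for the planned 80 subjects**, assuming all attend both visits:
- nominal: 80 × 56 = 4,480 days; 4,480 / 365.25 = 12.3 person-years
- shortest: 80 × 46 / 365.25 = 10.1 person-years
- longest: 80 × 66 / 365.25 = 14.5 person-years

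**Expected SAEs in that time.** The documents give no SAE rate, so 2 to 20 per 100 person-years is assumed:
- nominal gap: 12.27 × 0.02 = 0.25 and 12.27 × 0.20 = 2.45
- extremes of the windows: 10.1 × 0.02 = 0.2 and 14.5 × 0.20 = 2.9

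These are expected occurrences, not expected misses.

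**Which outputs are exposed?** Treatment-emergent AEs are defined by onset within 30 days of stopping drug (Protocol Section 8.5.2, SAP Section 7.1.5.1), or by having led to discontinuation of study drug. The primary safety endpoint is an AE leading to permanent discontinuation (Protocol Section 8.1.2). Neither depends materially on events after Day 30, and SVR12 does not depend on AE collection. What remains is the SAE and death listings and the all-deaths summary in SAP Section 7.1.6.

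**The case against.** The strongest reply is that Section 7.3 already governs. It treats AEs and SAEs under separate headings, footnote e matches the AE paragraph, and a footnote silent on SAEs does not cancel an explicit SAE rule. By lifting the duty to seek SAEs only after follow-up, Section 7.3 implies that sites should be seeking them until then. SAE reporting is also event-driven: it is due within 24 hours of the investigator's knowledge, whatever the visit schedule. Subjects see site staff at Week 12 anyway, and the eCRF completion guidelines, which are not among the documents, may contain a prompt.

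Much of this stands. SAEs after Day 30 remain reportable, and the share that would be missed cannot be estimated. The synopsis sentence may be no more than loose wording. SAP Section 2.2, which includes safety data through Week 12, prescribes no enquiry. The gap of a few days before Day 30 is small.

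It does not remove the point. The 24-hour clock starts only when the investigator knows of the event, and a scheduled question is how an investigator learns of an admission to another hospital. The implied duty to seek SAEs makes its absence from the schedule harder to defend. It is also odd that an unscheduled visit calls for AE information as a minimum while the last visit due for every subject does not.

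**Conclusion.** The point holds. Section 7.3 and footnote e give different impressions of when SAE capture ends, and no AE or SAE enquiry is scheduled in the last 56 days of follow-up (46 to 66). The day counts come directly from the schedule. The 12.3 person-years (10.1 to 14.5) assume the planned 80 subjects and full attendance. The SAE count of 0.2 to 2.5 rests wholly on an assumed rate and shows only that the number is small but need not be zero.

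The consequence is limited to the completeness of the SAE and death listings and the all-deaths summary. No efficacy result, primary safety result or treatment-emergent table is materially at risk. It is worth correcting because the remedy is cheap, not because it threatens the trial's conclusions.

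**What to change.** 1. In Protocol Section 6.3.2, Protocol Appendix 2 and SAP Appendix 1, add an enquiry at posttreatment Week 12. It should cover all SAEs and deaths since the previous visit, and any AE not yet recorded that began within 30 days of last dose.
2. Reword footnote e in both documents to give both periods: AEs and concomitant medications to 30 days after last dose; SAEs from consent through the posttreatment Week 12 visit, with a reference to Section 7.3. The footnote should also except medications given to treat an SAE, because Section 7.3 requires these to be recorded, while footnote e and Section 5.4 end medication collection at 30 days.
3. Align the synopsis safety line with the same two periods.
4. Leave the 30-day treatment-emergent definition and SAP Table 2 unchanged.

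The cost is one question at an existing visit, with no new visit or sample. Because the protocol changes, it needs an amendment with documented IRB/IEC approval before implementation (Sections 9.1.3 and 9.2.1), a matching edit to the SAP appendix, and an eCRF prompt if none exists.
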